10.2 Research Ethics Committee (REC) and other Regulatory review & reports

Before the start of the study, a favourable opinion will be sought from a London REC for the study protocol, informed consent forms and participant information sheets. Substantial amendments that require review by NHS REC will not be implemented until that review is in place and other mechanisms are in place to implement at site. All correspondence with the REC will be retained.

It is the Chief Investigator's responsibility to produce the annual reports as required. The Chief Investigator will notify the REC of the end of the study. An annual progress report (APR) will be submitted to the REC within 30 days of the 12-month anniversary date on which the favourable opinion was given, and annually until the study is declared ended.

Should the study end prematurely, the Chief Investigator will notify the REC, including the reasons for the premature termination. Within one year after the end of the study, the Chief Investigator will submit a final report with the results, including any publications/abstracts, to the REC.

Regulatory Review & Compliance

If an amendment to the protocol is necessary, the Chief Investigator will consult with the sponsor for an opinion on whether it should be considered a minor or a substantial amendment for the purposes of the REC. The necessary paperwork and supporting documents will be passed to the sponsor. Amendments will be submitted to the REC for consideration by the sponsor, and to our funding body,

16

Longitudinal
Outcomes of Gender
Identity in Children

The Tavistock and Portman
NHS Foundation Trust

NIHR. If ethical approval for the amendment is granted, the R&D department will be notified of the

 $change(s) \ by \ the \ research \ team \ overseen \ by \ the \ Chief \ Investigator.$

All amendments to the protocol shall be tracked in a log at the end of the protocol; a copy of this log will

be stored with the current and superseded protocols in the appropriate folder in the Trial Management

File.

10.3 Peer review

The study was submitted and successfully received NIHR funding. As part of this screening process, it

has undergone extensive peer-reviewed by external peer-reviewers.

10.4 Patient & Public Involvement

The study was developed in collaboration with a service user co-applicant; UK GID service users; and

external stakeholders, including voluntary user organisations.

The core research team includes a peer researcher as a co-applicant: a transgender young person and

research assistant with both experience of children and young people and Adult GID services and an

active interest in research.

Following the NIHR funding call, children/young people and their families using the UK GID service

were consulted regarding their priorities for research. At GID Service User Family Days in London

(7th August 2017) and Leeds (30th August 2017), the HS&DR funding call was presented and

feedback was requested on research questions/priorities families viewed as important, attendees were

also asked to complete a short questionnaire. Following the development of the proposal, a draft was

shared with three parents of young people accessing the service. Among this group, the major area of

interest to emerge in discussion was the need to focus research on the co-occurrence of ASD and GD.

The service has strong links with external stakeholders including voluntary organisations, who have

been consulted regarding the proposed research questions and priorities. An external stakeholder event

was hosted at the Tavistock on Feb 2nd 2018 bringing together community organisations, youth

groups, education and health. Summaries of the research were distributed and the feedback was

overwhelmingly positive with many indicating that the proposed research was 'long overdue'.

17

The Tavistock and Portman

NHS Foundation Trust

Several key service user organisations have indicated their interest and willingness to be represented on the external advisory group and/or provide input to the research. Training will be provided for these advisory group members and they will be paid for time attending meetings (at INVOLVE rates) and reimbursed for travel and additional expenses. Childcare will be provided if required. The external stakeholder advisory group will meet every 6-8 months.

In addition a Children and Young Persons advisory group will meet 6 monthly hosted by the UK GIDS service and Trust PPI (which has developed innovative methods of engaging young people e.g. in 'Pizza and chat' sessions where a local pizza company provides Pizza). A parent advisory group comprised of parents attending the service will meet 6 monthly. Trust PPI has an active well-staffed department that will provide training and support in the running of these groups and will link closely with the research team and GID service. We will ensure BAME representation on all advisory groups and will also link with existing BAME GID user support groups in order to ensure BAME input to the design and conduct of the study.

Funding has been allocated to develop a study website and multi-media resources which will be developed in consultation with key stakeholders and will aim to convey, in a child and family centred way, the 'human stories behind the figures'. Such resources will also assist in the education of NHS commissioners and clinicians schools and other relevant service providers and thereby help enhance support for children/young people and their families. PPI groups will be closely involved in the development of these resources and other activities and events.

10.5 Protocol compliance

The study will be overseen at each site by the Chief Investigator who will be familiar with the study protocol. Researchers already have appropriate experience in conducting research, and will receive the necessary training and supervision in order to carry out the research in each stage as per the protocol. All protocol breaches will be recorded using the appropriate documentation and reported to the Chief Investigator and Sponsor immediately.

Where a deviation from the protocol is reported on more than one occasion, the Chief Investigator and the Sponsor will liaise to investigate the reason for the breach, and suggest changes to ensure that it

does not recur. Should the change require an amendment to the protocol, an application will be made to the REC.

10.6 Data protection and patient confidentiality

a) Quantitative study

Personal data provided during assessments will be pseudonymised and not be used or disclosed in any form that might identify the participant. Pseudonyms will be held in a password protected database on an encrypted NHS server at the Tavistock and Portman NHS Foundation Trust, accessible solely to the chief investigator and immediate research team.

The online database used for quantitative assessments will be prepared for electronic use by the PRIMENT Clinical Trials Unit with technical support from *Sealed Envelope*, an independent company which provides *Red Pill*, a secure online data management system that collects and manages data in partnership with PRIMENT's data management team. All access will be via encrypted channels and limited to the research teams. Sealed Envelope is registered as a data controller with the UK Information Commissioner's Office (ICO) and has been inspected by the MHRA, the UK clinical trials regulator. Sealed Envelope has been assessed by PRIMENT to ensure that adequate processes are in place and are being followed for quality management, software development and security. There will be an agreement in place between UCL and Sealed Envelope to ensure compliance and agreement with clinical trial regulations and data protection laws.

A Data Protection Impact Assessment was carried out on the study assessing identified risks, likelihood of harm, severity of harm, mitigation and overall risk. Information with regards to the study participants will be kept confidential and managed in accordance with the GDPR, NHS Caldicott Guardians, Research Governance Framework for Health and Social Care and the Research Ethics Committee approval.

Analysis of assessment data will be carried out by the UCL PRIMENT team. PRIMENT is composed of experts in both statistical analysis and handling very sensitive data (they are one of the main centres for clinical trial handling at UCL-Royal Free). The 'Statistician' role on the Red Pill database will be used to download data directly from *Red Pill* for analysis. An 'Archivist Role' has been created on Red Pill that allows complete data downloads for ongoing studies for disaster recovery and database closure purposes. Red Pill archives contain data in csv, Stata and MySQL script formats. They also contain

audit logs, a data dictionary and a log of which users have been assigned permission to the Red Pill database whilst in use. Data is downloaded on a monthly basis by PRIMENT as part of the unit's back-up processes. Access is secured via an institutional firewall and restricted to authorized members of the research team. A Data Processing Agreement has been set up between the Trust and UCL and is currently undergoing authorisation.

b) Qualitative study

All digital data files (including audio files) will be assigned a pseudocode and uploaded onto a secure NHS server as soon as possible after data is collected, and the files deleted from the audio recorder memory disk or hard drive. Memory disks and hard drives containing data will be held in locked cabinets if it is not possible to upload the files immediately following data collection. The names of people and/or places mentioned during the interviews will be removed from transcripts before analysis and storage.

Pseudonyms/identity codes will be held in a password protected database on an encrypted NHS server at the Tavistock and Portman NHS Foundation Trust. Audio recordings will be transferred to a trusted transcription company using secure data transfer methods for transcription. Only the Chief Investigator and researchers will have access to assessments and audiorecordings. All members of the research team will be reminded of their duty to observe the NHS code of ethics regarding patient confidentiality. Monitors and auditors from the sponsor and regulatory authorities will have access to the participants' personal data if required. This is detailed in the subject information sheet and consent for this will be obtained from the participant.

10.7 Indemnity

As the Tavistock and Portman NHS Foundation Trust will act as sponsors, indemnity is provided through NHS schemes under Clinical Negligence Scheme for Trusts (CNST). Insurance or indemnity for the design of the protocol will be provided through NHS schemes (CNST).

10.8 Access to the final study dataset

The Chief Investigator and researchers including statisticians and health economist will have access to the final full dataset. Any other person wishing to have access to the full dataset must submit a formal request to the Chief Investigator for approval.

The Tavistock and Portman
NHS Foundation Trust

11 DISSEMINIATION POLICY

11.1 Dissemination policy

Intellectual property rights relating to the data arising from the study shall be held by the Tavistock & Portman NHS Foundation Trust.

Following the completion of the studies, data will be meticulously analysed. Findings will be tabulated and detailed in publications.

NIHR will be informed about all outputs resulting from the funded project at least 28 days prior to publication.

Consent to publish study data may be granted to co-investigators by the Tavistock & Portman NHS Foundation Trust.

All dissemination arising from the study must contain details of NIHR as the funder of the study, along with the standard disclaimer.

Participants who consent to receive the study findings will be sent an electronic or hard copy interim report and a final lay summary of the findings, depending on their preferred method of communication. They will also be provided with the details of where to access the online publication of the full study report.

11.2 Authorship eligibility guidelines and any intended use of professional writers

In partnership with the core study team of co-applicants, the Chief Investigator will make the decision regarding authorship for any peer-reviewed articles. All authors will be individually named.

The Tavistock and Portman NHS Foundation Trust

13. APPENDICES

Appendix 1 – Amendment History

Amendment No.	Protocol version no.	Date issued	Author(s) of changes	Details of changes made
1	2.0	18.07.2019		All sections that refer to the sample; which has been amended to 3-12 year olds at age of referral across the entire referral waiting list. Sections most extensively changed are: 9.1.1 (Inclusion criteria), 9.1.2 (Exclusion criteria), 9.2.2 (Sampling technique), and 9.3.1 (Sample identification). REC & HRA approval granted 29.08.2019
2	2.1	18.07.2019		Changes to sections 9.3.1 (sample identification) and 9.3.2 (consent stages), both in relation to how participants are identified and who contacts participants in the quantitative study. REC & HRA unfavourable opinion given 27.08.2019
3	2.2	16.09.2019		All sections that refer to the sample; which has been amended to 3-13 year olds at age of referral across the entire referral waiting list. Sections most extensively changed are: 9.1.1 (Inclusion criteria), 9.1.2 (Exclusion criteria), 9.2.2 (Sampling technique), and 9.3.1 (Sample identification).

Appendix 2 – Proposed timeline (please see attached document)

Appendix 3 – Table of procedures and measures

Intervention or procedure	Total no. of interventions or procedures	Average time taken per intervention or procedure	Who will conduct intervention or procedure
Information provision by phone (all appropriate referrals)	1	10 mins	GIDS team member
Information provision by phone (families agreed to be contacted)	1	20 mins	Appropriately trained researcher at Tavistock & Portman
Questionnaire assessment for all parents/carers completed at T0, T1 and T2:	3	40 - 60 mins	Self-report

- Demographics/Background			
(Parent age; Parent gender			
identification; Parent			
employment status; Parent			
education level; Parent			
ethnicity; Parent sexual			
orientation; Child age; Child			
birth assigned sex; Child			
ethnicity; Family living			
situation; Household			
composition; Marital status)			
- Child Gender			
Questionnaire for Parents			
(DSM Criteria for Gender			
Dysphoria; Gender Identity;			
Background to Referral;			
Social Transition; Body			
Image & Distress)			
- Strengths & Difficulties			
· ·			
Questionnaire (SDQ; Brief			
Emotional and Behavioural			
Screener)			
- Child Behaviour Checklist			
(CBCL; Emotional and			
Behavioural Functioning)			
- Autism Quotient 50 item			
scale (AQ; Child (age 4-11) or Adolescent (age 12-15)			
version; Autism Traits)			
- Child and Adolescent			
Service Use Schedule (CA-			
SUS; Health care resource			
use)			
Questions relating to healthcare			
resource use will be adapted by			
[name] (Health Economist)			
, , ,		20 :	
Additional questionnaire assessment	Dependent on	20 mins	Parent proxy report
for parents/carers of children who	age/competence		
are under 12, or refuse to participate but agree to parent/carer	of child at each		
participating, or are lacking capacity	time point (between 0 and		
complete self-report measures at T0,	3)		
T1, or T2:			
- Kidscreen 52 items-			
parental proxy			
(KIDSCREEN-52; Child			
health and well-being)			
U		1	

Identity in Children	1	T	
- Child Health Utility 9			
Dimensions - parental proxy			
(CHU-9D; Quality of life)			
Interview and guided assessment for	Dependent on	60 mins	Self-report
children aged 3-11 years with	age/competence	0 0	and or pro-
capacity to participate at T0, T1, or	of child at each		
T2:	time point		
- Children's Gender Identity	(between 0 and		
Semi-Structured Interview	3)		
- Gender Similarity Task			
- Child and Youth Resilience			
Measure (CYRM)			
- Child Health Utility 9			
Dimensions (CHU-9D)			
Dimensions (CHO-9D)			
Questionnaire assessment for	Dependent on	60 mins	Self-report
children over 12 years with capacity	age/competence		
to self-complete at T0, T1, or T2:	of child at each		
- Gender dysphoria	time point		
questionnaire (GDQ)	(between 0 and		
- Young Persons Gender	3)		
Questionnaire (DSM			
Criteria for Gender			
Dysphoria; Gender Identity;			
Background to Referral;			
Social Transition; Body			
Image & Distress;			
Relationships & Attraction)			
- Utrecht Gender Dysphoria			
Scale (UGDS; Gender			
Dysphoria Scale\)			
- Strengths and Difficulties			
Questionnaire (SDQ; brief emotional and behavioural			
screener)			
- Moods and Feelings			
Questionnaire (MFQ;			
depressive symptoms)			
- Child and Youth Resilience			
Measure (CYRM; social-			
ecological resilience)			
- Gender Identity Self			
Stigma Scale (internalised			
stigma and transphobia)			
- Kidscreen 52 items			
(KIDSCREEN-52; Child			
health and well-being)			

Identity in Children			
 Warwick-Edinburgh Mental Wellbeing Scale (WEMWBS; Mental wellbeing) Child Health Utility 9 Dimensions (CHU-9D; Quality of life) Youth Self Report (YSR; Emotional and Behavioral Functioning) 			
Physiological assessment for all participants, including those not going to a clinic: - Parents heights (at start) - Child's height - Child's weight - Child's pubertal development (RCPCH guidance on measuring puberty phase) - BMI All of the above are self-measured or measured with assistance from a parent/carer at each assessment (T0, T1, T2) using simple instructions provided by research team	3	5 – 10 mins	Self-measured
(Request for routinely collected data – not part of intervention research) Physiological assessment for participants (children and young people) receiving physical treatment with hormone blockers (GnRH agonists) and/or cross-sex hormones: - Parent's heights (Clinical measure) - CYP height, sitting height, bi-acromial width, bi-iliac width, weight (clinical measures) - BMI (value derived by calculation) - Pubertal Tanner staging (Clinical examination)	3	N/A	University College London Hospitals (UCLH) NHS Foundation Trust

- Body composition (Tanita bioelectrical impedance analyser)	
Radiological measures - Bone densitometry (Dexa Scan) - Bone age (X-ray of left hand & wrist)	
General blood and endocrine measures - Full blood count, ferritin (iron) - Renal, liver, lipid and bone profiles - Vitamin D - Thyroid function - Reproductive hormones (FSH, LH, PRL, Testosterone, Oestradiol)

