association between the pre-specified explanatory variables and persistent or ongoing GD. Appropriate regression models will be used to investigate the explanatory variables for the secondary outcomes, physical/endocrine intervention, Mental Health (SDQ), Behavioural and Emotional Functioning (CBCL, YSR) and Quality of Life (Kidscreen 52, CHU-9D). Models will account for the repeated measures of Mental Health and Behavioural and Emotional functioning and quality of life outcomes and the relevant explanatory variables. Exploratory subgroup analyses will be carried out for the prepubertal children and children with autistic traits (as assessed using the AQ) using descriptive statistics and appropriate regression models, where possible. Physical and psychological health outcomes over time will be compared descriptively between those in receipt of hormone blockers (GnRH agonists) and those of a similar age/pubertal stage who progress through puberty without such intervention.

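### Appendix 3 leaves 12-year-olds with no KIDSCREEN-52 or CHU-9D as worded, and KIDSCREEN-52 passes from parent to child report at 12 with no overlap

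*Protocol*

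**What the plan says.** Appendix 3 of the protocol assigns questionnaires in blocks.

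- **All parents, no age limit.** The parent gender questionnaire with DSM criteria, SDQ, CBCL, the autism questionnaire (AQ) and the service-use schedule come from all "parents/carers completed at T0, T1 and T2".
- **Parent proxy.** KIDSCREEN-52 and CHU-9D by proxy are for children who "are under 12, or refuse to participate but agree to parent/carer" participation, or who lack the capacity to self-report.
- **Younger child, guided.** For "children aged 3-11 years with" capacity. It includes CHU-9D but not KIDSCREEN-52.
- **Older child, self-report.** For "children over 12 years with capacity". It includes KIDSCREEN-52, CHU-9D, SDQ and YSR.

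The child and proxy blocks are chosen afresh at each visit; the guided block, for example, depends on "capacity to participate at T0, T1, or" T2. The AQ line in the same table splits elsewhere: "scale (AQ; Child (age 4-11) or Adolescent (age 12-15".

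Section 7(a) names the secondary outcomes as "Mental Health (SDQ), Behavioural and Emotional Functioning (CBCL, YSR) and Quality of Life (Kidscreen 52, CHU-9D" and adds: "Models will account for the repeated measures of Mental Health and Behavioural and Emotional functioning and quality of life outcomes". It builds QALYs from CHU-9D by area under the curve. It names no reporter for any of these and defers detail to a statistical analysis plan.

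**The concern.** There are two separate problems, and both lie in what is collected.

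First, one block ends below 12, one ends at 11, and the third begins above 12. If site staff or the online database apply these limits in whole years, a 12-year-old with capacity is offered no KIDSCREEN-52 and no CHU-9D, by proxy or by self-report. A missing CHU-9D at one of three visits also leaves that child without a complete area-under-the-curve QALY.

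Second, even with the limits repaired, KIDSCREEN-52 has no single-informant series for a child with capacity who passes 12 during follow-up. The parent answers before and the child answers after, and no visit has both. Any systematic difference between parent and child answers then enters the child's trajectory as apparent change. Research question 3 asks about the effect of physical treatment and social transition on quality of life, and section 2 refers to physical treatment starting in early puberty. The change of informant can therefore fall close in time to the exposures of interest.

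An analysis plan written later can choose among the data collected, but it cannot recover a proxy form that was never completed.

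**Working it through.** The protocol gives no figure on this point to reproduce. The check sets the bands side by side and then counts children under stated assumptions.

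**Step 1: who reports KIDSCREEN-52.** Take a child with capacity and visits exactly one year apart (sections 3.1 and 5), with age in whole years.

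| Age at T0 | Bands as worded (T0, T1, T2) | Age 12 placed in the older block (T0, T1, T2) |
|---|---|---|
| 9 or under | proxy, proxy, proxy | proxy, proxy, proxy |
| 10 | proxy, proxy, none | proxy, proxy, self |
| 11 | proxy, none, self | proxy, self, self |
| 12 | none, self, self | self, self, self |
| 13 | self, self, self | self, self, self |

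**Step 2: the other modelled outcomes.** Of the five instruments in section 7(a), SDQ and CBCL have a parent version at every visit. YSR exists only in the older block, so it starts there and does not switch. CHU-9D has child report in both child blocks, so a child with capacity can stay on self-report apart from the literal gap at 12; below 12 the proxy is collected as well. Only KIDSCREEN-52 is forced to change informant.

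**Step 3: shares.** The protocol gives no age distribution. Assume uniform ages 3 to 13 at T0, which is 11 single-year ages.

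- Bands as worded, one visit at age 12 without these measures (ages 10, 11, 12): 3/11 = 27%, about 139 of the 510 expected to complete follow-up.
- Bands as worded, change of KIDSCREEN-52 informant (age 11 only): 1/11 = 9%.
- Contiguous bands, crossing 12 (ages 10 and 11): 2/11 = 18%, about 93 of 510.
- Contiguous bands, visit lost to the gap: 0.

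**Step 4: sensitivity.** Ages 3 to 13 are ages at referral acceptance, and recruitment includes a waiting list of 585 (section 9.2.2), so ages at T0 will be higher. Section 9.1.2 also excludes those aged 13 or older at referral.

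| Assumed ages at T0 | Visit at age 12 | Cross 12 |
|---|---|---|
| Uniform 3-13 | 3/11 = 27% | 2/11 = 18% |
| Uniform 3-12 | 3/10 = 30% | 2/10 = 20% |
| 3-13, weight (age - 2) | 27/66 = 41% | 17/66 = 26% |
| Same, then 2 years older | 21/66 = 32% | 13/66 = 20% |
| 3-12, weight (age - 2) squared | 245/385 = 64% | 145/385 = 38% |

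The middle column matters only on the literal bands, the last only on contiguous bands.

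**Step 5: size of the artefact.** If proxy and self-report differ by d SD and the model ignores informant, a switcher shows a false change of d, and the cohort mean shifts by (share crossing) × d. For an assumed d of 0.2 to 0.5 SD this runs from 0.182 × 0.2 = 0.04 SD to 0.377 × 0.5 = 0.19 SD. The documents give no value for d.

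**Step 6: would a reporter term suffice?** Apart from older children who refuse or lack capacity, informant is fixed by age. The term would be estimated from a step at 12 plus a selected group, so it would separate informant from age poorly.

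**The case against.** A reader might infer that the repeated-measures analyses as a whole will confuse informant with change. The documents do not support that. Parent SDQ, CBCL and the parent gender questionnaire keep one informant throughout, and CHU-9D child report is available on both sides of 12. Nothing in section 7 says that proxy and self-report scores, or CBCL and YSR, will be joined in one series. The choice of reporter and any reporter term can properly wait for the analysis plan. Ongoing gender dysphoria is analysed by logistic regression, so the repeated-measures argument does not reach it directly. Listing YSR beside CBCL is not an error.

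The gap at 12 is probably a slip: the AQ line places 12 in the older group, and the self-report limit can be read as past the twelfth birthday. Children of 12 who refuse or lack capacity get the proxy in any case.

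It is also tempting to say that 18% switch and, in addition, 27% lose a visit. Those need incompatible readings of age 12.

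On confounding, the hormone-blocker comparison in section 7(a) is descriptive and against children of similar age or pubertal stage, so both groups largely share the same reporter. That weakens the argument for that comparison, but not for change over time in the regression models.

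All of this stands. It does not remove the need for one unambiguous collection rule, nor does it give KIDSCREEN-52 a continuous informant. Both depend on Appendix 3, not on the analysis plan.

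**Conclusion.** The point holds in two limited parts. As worded, Appendix 3 gives a 12-year-old with capacity no KIDSCREEN-52 or CHU-9D from any reporter; the likely intent is that 12 belongs to the older block. And KIDSCREEN-52 changes informant at 12 with no overlap for children with capacity, so the quality-of-life model risks reading parent-child disagreement as change.

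Under uniform ages 3 to 13 at T0, either about 27% have a visit without these measures (literal bands, with capacity) or about 18% cross 12 (contiguous bands). The assumed age distributions tried give 27% to 64% and 18% to 38% respectively. The age distribution and the proxy-self gap are assumptions, so the defect in the collection rule is certain while its numerical effect is not. It should be corrected because the repair is cheap and a missed visit cannot be recovered.

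**What to change.** 1. In Appendix 3, reword the lower limit of the self-report block from over 12 years to 12 years and over, and check that the online database applies the same limit. This costs nothing beyond the wording.
2. Have parents complete the proxy KIDSCREEN-52 at T0, T1 and T2 whatever the child's age, with self-report from 12 in addition. One informant series then runs through all three visits, and the overlap lets the proxy-self difference be estimated instead of assumed. The cost is part of a proxy block put at 20 minutes, for parents of older children.
3. State that each child's QALY uses one CHU-9D reporter across the three visits.
4. State that YSR is analysed in those aged 12 and over.

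Whether parent report should lead for every outcome, and whether to add a reporter term, are choices for the analysis plan and are not required by this point.
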